**A PHASE 1/2, TWO-CENTER, DOUBLE-BLIND, RANDOMIZED, PLACEBO-
CONTROLLED MULTI-PERIOD CROSSOVER (N-OF-1) STUDY TO EVALUATE THE
FEASIBILITY, SAFETY, AND EFFICACY OF TJ-68 IN PATIENTS WITH AMYOTROPHIC
LATERAL SCLEROSIS (ALS) AND MUSCLE CRAMPS**

NCT04998305

June 27, 2024

1. Background

This is the statistical analysis plan for a phase 1/2 trial of TJ-68 in participants with amyotrophic lateral sclerosis (ALS) and muscle cramps. This trial aims to evaluate the efficacy of TJ-68 for improving muscle cramps in the participants using a double-blind, randomized, crossover design. This trial also aims to evaluate safety of TJ-68.

2. Study Design

2.1. Design Overview

This is a multi-period crossover study where each participant will receive four 2-week treatment periods of TJ-68/placebo. We plan to randomize a total of 26 participants, with 13 randomized to Treatment Sequence A: TJ-68-Placebo-Placebo-TJ-68, and another 13 to Treatment Sequence B: Placebo-TJ-68-TJ-68-Placebo, with a 1-week washout period between treatment periods. That is, each participant will receive TJ-68 and Placebo each in two separate treatment periods. Assuming 15% attrition, we expect to have 22 evaluable participants. Balanced randomization of the two alternating treatment sequences will eliminate linear trend in the primary analysis.

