3.1. Primary Outcome

The primary outcome of the study will be calculated using the Columbia Muscle Cramp Scale (MCS). We will use MCS item #5, visual analog scale (VAS) (0-10) for Muscle Cramps Affecting Overall Daily Activity of Columbia MCS as the primary outcome. The MCS will be assessed on the phone twice a week; thus, there will be a total of four MCS assessments per treatment period. However, for the primary analysis, only data in the second week of each treatment period will be used to minimize carryover effects.

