3.2. Statistical Analysis for the Primary Outcome

The primary analysis will be performed using linear mixed effect (LME) model to estimate the effect of TJ-68 compared to placebo on MCS VAS. The LME model will use all available MCS VAS measured in the second week of all treatment periods per mITT. The model will include TJ-68 as a main effect with a random participant effect to account for within-individual correlation. While balanced randomization of Treatment Sequences A and B will eliminate linear time trend, we will also explore linear and non-linear time effects in the LME model to explore the impact on the primary comparison between TJ-68 and Placebo.

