3.3. Sample Size Consideration

We aim to enroll 22 evaluable participants equally to the two alternating TJ-68/Placebo sequences over the four treatment periods, i.e., each participant will have 4 observations. Under the LME model, assuming a within-participant standard deviation of 1.4 based on our pilot data, this sample size will yield about 85% power to detect a 1-point shift on MCS VAS. Assuming 15% attrition, we will plan to enroll a total of 22 participants.

4. Safety Analysis

Adverse events (AE), including the presence of hypokalemia, will be summarized by treatment per participant. The AE will be attributed to the period in which it is observed. AE rate by treatment will be summarized using proportion and 95% confidence intervals and will be compared using McNemar test. Longitudinal AE data will be modeled using generalized linear mixed effect model with a logit link.

5. Secondary Outcome Analyses

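### The primary mixed model omits period because sequence balance removes a linear trend; that protects the estimate in completers but not its standard error, and period should be added together with a rule for the two second-week values

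*Combined protocol and SAP*

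**What the plan says.** The two sequences are TJ-68, placebo, placebo, TJ-68 and its mirror image (SAP 2.1). On time trends 2.1 says: "Balanced randomization of the two alternating treatment sequences will eliminate linear trend in the primary analysis".

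Section 3.2 specifies the primary model: "The model will include TJ-68 as a main effect with a random participant effect to account for within-individual correlation". Time terms are left to exploration: "While balanced randomization of Treatment Sequences A and B will eliminate linear time trend, we will also explore linear and non-linear time effects". Nothing says that the primary test or interval will be adjusted for period.

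The sections differ on how many values enter the model. Section 3.3 assumes that "each participant will have 4 observations", which is one per period. Section 3.1 says: "The MCS will be assessed on the phone twice a week; thus, there will be a total of four MCS assessments per treatment period", and restricts the primary analysis to the second week. Section 3.2 adds: "The LME model will use all available MCS VAS measured in the second week of all treatment periods per mITT". Read together, 3.1 and 3.2 give up to two values per period, or eight per completer.

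The power statement in 3.3 is that "this sample size will yield about 85% power to detect a 1-point shift on MCS VAS", "assuming a within-participant standard deviation of 1.4 based on our pilot data".

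**The concern.** Removing a trend from an estimate is not the same as removing it from the analysis. A drift that cancels from the treatment contrast can still sit in the residual of a model with no time term. The estimator's true variance is then unchanged while its reported variance grows: the interval is too wide, the test is conservative and power is lost.

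The plan treats a trend as possible, since it relies on the design to remove one and intends to explore linear and non-linear forms. The four periods and three washouts span 4 × 2 + 3 = 11 weeks.

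The number of values per period matters because it can reverse the direction of the error. Two correlated values in a period, modelled as independent given the participant, make the SE too small. An edit that addressed period alone could therefore leave the larger problem in place.

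**Working it through.** **Inputs.** From the SAP: 22 evaluable participants, 11 per sequence; within-participant SD 1.4; 1-point effect; four periods. Assumed, because the SAP gives no figure: two-sided alpha 0.05, drift b in points per period, and within-period correlation ρ.

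**1. The plan's own power figure.** With one value per period, a completer's contrast (mean of two TJ-68 periods minus mean of two placebo periods) has variance 1.4² × (1/2 + 1/2) = 1.96. So SE = 1.4/√22 = 0.298. Power is Φ(1/0.2985 − 1.96) = Φ(1.39) = 91.8%, or 91.0% by noncentral t on 65 df. The stated 85% is not reproduced at 22; about 85% appears at 18 to 18.7 participants (22 × 0.85 = 18.7). That is a separate matter, and nothing below depends on it.

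**2. The estimate.** Centre time as (−1.5, −0.5, 0.5, 1.5). The contrast (+1, −1, −1, +1) gives −1.5 + 0.5 − 0.5 + 1.5 = 0. A linear trend cancels within every four-period completer.

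**3. The standard error, one value per period.** The squared time scores sum to 5, so drift adds 5 × 22 × b² to the residual sum of squares, on 88 − 22 − 1 = 65 df. Reported SE = √{[1.96 + 110b²/65]/22}. At b = 0.5 this is √(2.383/22) = 0.329. The true SE is 0.298 throughout.

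| b | SE without period | Power without period | Type I error without period |
|---|---|---|---|
| 0 | 0.298 | 91% | 5.0% |
| 0.2 | 0.304 | 90% | 4.6% |
| 0.5 | 0.329 | 87% | 3.1% |
| 0.75 | 0.364 | 82% | 1.7% |
| 1.0 | 0.407 | 73% | 0.8% |

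With categorical period (62 df), power is about 91% and type I error 5.0% in every row. Without it, power is 85.2% at b = 0.61 and 84.95% at b = 0.62, a drift of 3 × 0.62 = 1.9 points from first to last period.

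**4. If the pilot SD already contains the drift.** Four equally spaced periods with slope b contribute (5/3)b² to the within-participant variance, so the drift-free variance is 1.96 − (5/3)b². The SD becomes 1.376, 1.242 and 1.011 at b = 0.2, 0.5 and 0.75. Power is 91%, 93% and 97% without period, and 92%, 96% and 99.5% with it.

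**5. If slopes differ between participants.** With mean slope 0.5 and slope SD 0.5 (assumed; 20,000 simulated trials), the SE is 0.356 without period and 0.328 with it, and power is 82.5% and 87.1%. With mean slope 0 and slope SD 0.75, period recovers nothing: SE 0.362 and power about 82% either way.

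**6. Two values per period, participant random effect only.** Take 1.96 as the variance of a single call. At ρ = 0.5 a period mean has variance 1.96 × 0.75 = 1.47, so the true SE is √(1.47/22) = 0.258. With no drift and no period term, the model's expected residual mean square is (2 × 1.47 × 65 + 1.96 × 0.5 × 88)/153 = 1.813, and its SE is √(1.813/44) = 0.203. Type I error at ρ = 0.5:

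| b | Without period | Period only | Period plus averaging |
|---|---|---|---|
| 0 | 12.4% | 12.6% | 5.0% |
| 0.2 | 11.8% | 12.6% | 5.0% |
| 0.5 | 9.2% | 12.6% | 5.0% |
| 0.75 | 6.5% | 12.6% | 5.0% |
| 1.0 | 4.0% | 12.6% | 5.0% |

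With period only, type I error is 5.0%, 8.6% and 16.7% at ρ = 0, 0.25 and 0.75.

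**7. Power after averaging.** With period in the model and ρ = 0.5, power is about 97% if 1.4 is the SD of a single call (period-mean SD √1.47 = 1.21), and 91% if 1.4 is already the SD of a period mean. The SAP does not say which.

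**8. Dropout.** A participant stopping after period 3 contributes a trend error of −1.5b in one sequence and +1.5b in the other. Four such dropouts among 26, unrelated to sequence, give a mean absolute bias of 0.050 to 0.056 × b, about 0.03 points at b = 0.5. It is zero if they split 2 and 2.

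**The case against.** The best defence is that the plan's sentence is correct where it matters most. The estimate is protected in completers, and the error from omitting period runs in the conservative direction, so this mechanism alone creates no excess false positives. The loss is negligible at 0.2 points per period. Falling below 85% needs a drift over the trial of nearly twice the effect sought, and there is no shortfall against 85% if the pilot SD already includes drift. Sections 2.3 and 3.2 also plan exploratory time models, a completers analysis and a comparison of missingness by sequence and period. All of that stands, and it limits how much weight the point deserves. What it does not do is change the primary test, which remains unadjusted whatever the exploratory models show.

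Three stronger readings are tempting, and the documents do not support them.

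- A reader might infer that the reported SE will be too wide under the model as written. That follows only from one value per period in 3.3. Under 3.1 with 3.2, the SE is too narrow at ρ = 0.5 for every drift in the table up to 0.75.
- A reader might take the inflated type I error as a result of leaving period out. It comes from treating correlated values within a period as independent, and adding period alone does not reduce it.
- A reader might expect a period term to recover all power lost to drift. It removes only the part common to participants.

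**Conclusion.** The point holds in conditional form. The claim about a linear trend in 2.1 and 3.2 is right for the estimate in four-period completers and wrong as a reason to leave the SE unadjusted. Given one value per period and a common drift, the test is conservative. The loss is about 4 power points at 0.5 points per period and 18 at 1.0 (91% against 87% and 73%). Given two positively correlated values per period, the larger risk is a type I error above 5%, whether or not period is added.

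The sizes rest on assumed slopes, correlation and alpha. The arithmetic on which way each mechanism pushes the SE does not. Dropout bias is minor. I rank this as a cheap improvement: the likely gain may be modest, but with no drift the period term has no visible power cost, and the edit also settles how many values are analysed.

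**What to change.** In 3.2, pre-specify period (1 to 4, categorical) as a fixed effect in the primary model. In the same edit, either average the second-week values within each period or add a participant-by-period random effect. With complete data the two give the same treatment SE (0.2514 for both in one simulated data set, against 0.1959 with period and a participant effect only). Do not add period alone if both values enter the model.

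Make the number of values per participant agree across 3.1, 3.2 and 3.3, and state in 3.3 whether 1.4 is the SD of a single call or of a period mean, since any power figure for averaged values depends on it. Limit the trend wording in 2.1 and 3.2 to the point estimate in participants with all four periods. Keep the model without period as a sensitivity analysis.

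The cost is SAP wording and 3 residual degrees of freedom, 65 to 62 with 22 completers and one value or one average per period. No change to trial conduct is needed.

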2.2. Randomization Procedures

The 22 evaluable participants will be randomized 1:1 to the two treatment sequences based on the study schedule, using blocked randomization stratified by site. To ensure power with anticipated dropout (15%), we anticipate randomizing up to 2 additional participants to each treatment sequence.

2.3. Analysis Populations and Missing Data

All efficacy analyses will be performed using the modified intent-to-treat (mITT) population. The mITT population consists of all randomized participants with outcomes evaluated in at least two (out of four) post-randomization periods with at least one period in TJ-68 and one in Placebo.

As sensitivity analyses, we will also perform efficacy analyses in the completers only, that is, participants with outcome evaluated in all 4 treatment periods.

Safety analyses will be performed as treated.

Missing data patterns will be compared by treatment sequence as well as by the treatment periods. While the primary analyses will be performed in the mITT population defined above, we will perform sensitivity analyses using imputed data sets under different imputation approaches:

- (A) Mean imputations: Missing data within a treatment period will be imputed using averages from other data points within the same treatment period. If data in the entire treatment period is missing, the observations from the previous period will be carried forward.
- (B) Worst-outcome imputations: All missing data will be imputed using the worst values observed in a treatment group.

3. Primary Efficacy Analysis

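### The mITT rule discards first-period scores from participants who never reach the other treatment; if such dropout depends on the score and differs by sequence, the primary estimate is modestly biased, and a short edit removes this.

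*Combined protocol and SAP*

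**What the plan says.** Section 2.3 states: "All efficacy analyses will be performed using the modified intent-to-treat (mITT) population". It defines that population as the randomized participants "with outcomes evaluated in at least two (out of four) post-randomization periods with at least one period in TJ-68 and one in Placebo". Section 3.2 carries the rule into the primary model: "The LME model will use all available MCS VAS measured in the second week of all treatment periods per mITT". The model itself is simple: "The model will include TJ-68 as a main effect with a random participant effect to account for within-individual correlation". Time enters only in an exploratory way ("we will also explore linear and non-linear time effects in the LME model"), because the plan relies on the balance of the two sequences to remove a linear trend.

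Section 2.1 gives the design: "We plan to randomize a total of 26 participants", with "13 randomized to Treatment Sequence A: TJ-68-Placebo-Placebo-TJ-68" and "another 13 to Treatment Sequence B: Placebo-TJ-68-TJ-68-Placebo". Treatment thus changes between periods 1 and 2 in both arms. Section 3.1 restricts the primary analysis to second-week scores.

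Section 2.3 also plans a completer analysis, two imputation analyses, and a comparison of missing-data patterns by sequence and by period. It does not specify an analysis of everyone randomized with any observed outcome.

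**The concern.** Membership of the primary set is decided after randomization and can depend on response. A participant who completes period 1 and leaves before an evaluable period 2 is removed, along with a score that was validly recorded. If those who leave a TJ-68 first period are mainly poor scorers, the TJ-68 period-1 scores that remain look too good and the benefit is overstated. If the poor scorers leave after a placebo first period, the benefit is understated.

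A likelihood-based mixed model can use a participant with a single score. Under missing at random it needs that score to correct for dropout related to it, and the mITT rule withholds it. The completer set is narrower still, so it cannot reveal the problem.

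**Working it through.** **Inputs from the SAP.** 26 randomized, 13 per sequence, 15% attrition (0.15 × 26 = 3.9, so 4 leave and 22 remain; Section 2.1). Within-participant SD 1.4, target shift 1 point, four observations per participant (Section 3.3).

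**Assumptions.** Between-participant SD σb is not given; 1.4 to 2.0 is used. A higher VAS is worse, the true effect is −1, there is one score per period, all 4 leave after period 1, and everyone else completes.

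**Benchmark.** The plan gives no figure for this bias. With 22 completers there are 44 scores per treatment, so SE = 1.4 × √(2/44) = 0.298. At an assumed two-sided 0.05 this gives 91.8% power, so the plan's figure of about 85% for 22 evaluable is not reproduced. That is a separate matter and does not enter below.

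**Bias under mITT.** When all 22 have four scores, the treatment estimate is the average over participants of (mean of two TJ-68 scores − mean of two placebo scores). The period-1 score has weight +1/2 in TJ-68-first and −1/2 in placebo-first. Removing the k highest of 13 period-1 scores shifts the summed within-participant errors of those who stay by −S(k) × σw²/√(σw² + σb²). Here S(k) is the sum of the k largest expected normal order statistics for n = 13: S(1) = 1.668, S(3) = 3.682, S(4) = 4.285. Hence

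bias = −[S(k in TJ-68-first) − S(k in placebo-first)] / (2 × 22) × σw²/√(σw² + σb²).

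The last factor is 1.96/1.980 = 0.990 for σb = 1.4 and 1.96/2.441 = 0.803 for σb = 2.0. For a 4:0 split, 4.285/44 = 0.0974, which gives 0.078 to 0.096. For 3:1, (3.682 − 1.668)/44 = 0.0458, which gives 0.037 to 0.045.

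A simulation check used 8,000 trials per case and a random-intercept model with known variances:

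| Worst scorers leaving (TJ-68-first : placebo-first) | Bias by formula | mITT estimate | All available data |
|---|---|---|---|
| 4:0 | −0.078 to −0.096 | −1.08 to −1.10 | −1.00 |
| 0:4 | +0.078 to +0.096 | −0.92 to −0.90 | −1.00 |
| 3:1 | −0.037 to −0.045 | −1.04 | −1.00 |
| 2:2 | 0 | −1.00 | −1.00 |

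The SD of the estimate is about 0.30 in both analyses, so the largest bias in the table is 0.096/0.298, about one third of an SE.

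**Sensitivity to the assumptions.** If a single worst scorer leaves, the bias is 1.668/(2 × 25) × 0.803 to 0.990 = 0.027 to 0.033. In large-sample runs with σb from 1 to 3 and a hard cut-off applied in one sequence, it is 0.06 to 0.12. It reaches 0.16 only if σb is 1 and high scorers leave TJ-68 while low scorers leave placebo. One common cut-off in both sequences gives 0.01 to 0.05 with a 1-point effect and 0.00 with none.

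**Time trend.** A one-period participant breaks the within-participant balance that removes a linear trend. With an assumed trend of 0.5 points per period, no period term, and four placebo-first participants leaving at random, the all-data estimate is −0.97 to −0.98, against −1.00 for mITT. With categorical period terms, the all-data estimate is −1.00 in every case above, and the SD rises from about 0.299 to about 0.303 or 0.304. Adding period within mITT does not help: the 4:0 case then gives −1.10 to −1.12.

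**The case against.** The best defence is that requiring both treatments is common in crossover trials, the rule is prespecified, and the bias needs an unlikely pattern. Anyone evaluated in periods 1 and 2 stays in mITT, so only departures between those periods matter, and the documents say nothing about dropout timing. If dropout were unrelated to sequence, all four would come from one arm with probability 2 × C(13,4)/C(26,4) = 1,430/14,950, or 9.6%. When higher scorers are merely more likely to leave (σb = 2.0), the mITT and all-data estimates differ by about 0.05 for 4:0 and 0.025 for 3:1. Simulated type I error under mITT stays at 0.05 to 0.06. All this stands and limits the size of the point.

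A reader might infer that any dropout following the first-period response biases the estimate. It does not: equal selection in the two sequences cancels. A reader might also infer that including these participants costs nothing. Without a period term it can introduce a trend bias of up to about 0.04, so the period term belongs in the fix.

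The planned safeguards answer the point only in part. Comparing missing-data patterns could reveal asymmetric dropout but does not correct the estimate. Section 2.3 can be read as extending imputation beyond mITT, so it cannot be said that those analyses leave these participants out; the text is unclear. If they are included, carrying the previous period forward would place a period-1 score in a period on the opposite treatment.

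**Conclusion.** The point holds in a limited form. The mITT rule selects on a post-randomization event and discards recorded week-2 scores. This biases the primary estimate only when leaving depends on the period-1 score and differs by first treatment. In the extreme case the bias is about 0.08 to 0.10 points on a 1-point target, and it can go in either direction. The figure rests on the assumed between-participant SD, on all attrition falling after period 1, and on worst scorers leaving one sequence only.

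The documents contain no dropout data, so they do not support a claim that the result will be biased or that the trial's conclusion is unsafe. The case for change is that the exclusion buys no precision and is easily removed.

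**What to change.** In Section 2.3, define the primary efficacy set as all randomized participants with at least one post-randomization week-2 VAS. In Section 3.2, add period as a categorical fixed effect to the primary model. Keep the present mITT and completer sets as sensitivity analyses, and state that the imputation analyses also cover participants observed in only one period.

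The cost is one or two sentences and about 0.005 on the SD of the estimate. Two limits remain. The correction relies on missing at random, and a participant who leaves before any week-2 score is recovered by neither definition.

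### Imputation approach (A) fills periods 2 and 4 with a score from the other treatment, so part or all of any fall in that sensitivity estimate reflects mislabelled treatment, not missing data

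*Combined protocol and SAP*

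**What the plan says.** Section 2.1 fixes the treatment orders: "with 13 randomized to Treatment Sequence A: TJ-68-Placebo-Placebo-TJ-68, and another 13 to Treatment Sequence B: Placebo-TJ-68-TJ-68-Placebo". Section 2.3 admits a participant to mITT with outcomes in "at least two (out of four) post-randomization periods with at least one period in TJ-68 and one in Placebo", so participants with whole periods missing can stay in the analysis.

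The primary model (section 3.2) uses the available second-week scores without imputation. Section 2.3 then adds sensitivity analyses: completers only, and two imputation approaches. Approach (A) has two parts:

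- For partial gaps: "Missing data within a treatment period will be imputed using averages from other data points within the same treatment period".
- For whole periods: "If data in the entire treatment period is missing, the observations from the previous period will be carried forward".

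On the amount of loss, section 2.1 says "Assuming 15% attrition, we expect to have 22 evaluable participants", and section 2.2 allows for the same 15% dropout. Neither says when losses will occur. Section 2.3 also plans a description of missingness: "Missing data patterns will be compared by treatment sequence as well as by the treatment periods".

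**The concern.** Carrying the last value forward assumes that the earlier score is a fair stand-in for the missing one. In this crossover that is plausible only when both periods are on the same treatment. In each sequence the treatment changes between periods 1 and 2 and between periods 3 and 4, and stays the same only between periods 2 and 3. A missing period 2 or 4 is therefore always filled from the wrong treatment and analysed under the right label.

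This touches the dropouts the plan expects. A participant who leaves for good and still qualifies for mITT can have lost only period 4 or periods 3-4. The first is filled across treatments. The second is filled across treatments if the rule is chained. If it is not chained, period 4 has no value.

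At stake is what the sensitivity analysis can tell a reader. It should show whether the conclusion depends on how missing data are handled, but here the filling rule itself moves the estimate.

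**Working it through.** **Inputs.** Sequences, 26 randomized, 22 evaluable and 15% attrition (section 2.1); the mITT rule and approach (A) (section 2.3); within-participant SD 1.4 and a 1-point effect (section 3.3). Assumed for simulation only: placebo mean 5, between-participant SD 1.5, one week-2 value per period, two-sided 5% test.

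**The plan's own figure.** 26 × 0.85 = 22.1, so 22 evaluable and about 4 lost. This reproduces section 2.1.

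**Per participant.** In Sequence A the scores are T1, P2, P3, T4, and the effect is the TJ-68 mean minus the placebo mean. Sequence B mirrors it.

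| Missing | After approach (A) | Share of effect kept |
|---|---|---|
| Period 4 | (T1+P3)/2 − (P2+P3)/2 = (T1−P2)/2 | one half |
| Period 2 | (T1+T4)/2 − (T1+P3)/2 = (T4−P3)/2 | one half |
| Periods 3-4, chained | (T1+P2)/2 − P2 = (T1−P2)/2 | one half |
| Periods 2 and 4 | (T1+P3)/2 − (T1+P3)/2 = 0 | none |
| Period 3 | (T1+T4)/2 − P2 | all |
| Period 1, 1-2, or 1 and 3 | at least one period left empty | rule incomplete |

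These eight patterns are all the whole-period losses that mITT allows. Loss of periods 1 and 4, or 2 and 3, leaves only one treatment and excludes the participant. The halving holds in expectation, ignoring time trend and carryover. The zero is an identity.

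**Pooled.** Once every period is filled the design is balanced, so the treatment coefficient is the mean of the participants' differences.

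- All four stay in mITT and lose only period 4: (22 × 1 + 4 × 0.5)/26 = 0.923, a loss of 4/52 = 7.7%.
- Two stay in and two are outside mITT: (22 × 1 + 2 × 0.5)/24 = 0.958, a loss of 2/48 = 4.2%.
- All four are outside mITT: no loss.

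**Simulation.** With a true effect of −1 and four participants missing period 4 (two per sequence), the observed-data estimate averages −0.982 and approach (A) −0.907, a fall of 0.075/0.982 = 7.6%. With between-participant SD from 1 to 2 the loss stays at 7.6% to 7.7%. Power with all 26 in mITT falls from 94.0% to 92.4%. Under no effect, approach (A) rejects about 4.1% of the time in this pattern, and 3.9% to 5.9% across loss of period 2, 3, 4, 2 and 4, or 3-4.

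**Period 3.** The fill comes from the same treatment and does not dilute the effect, but the copy is counted as real data. With four participants affected, rejection under no effect is about 5.9%, against 4.8% on observed data.

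**The case against.** The strongest reply is that little depends on this. Approach (A) is one of three sensitivity analyses, beside the worst-outcome approach and completers only ("As sensitivity analyses, we will also perform efficacy analyses in the completers only"). The primary model never uses it, power barely moves, and false positives are not materially inflated. All of that stands, and it limits the point to interpretation.

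Second, 7.7% assumes that all four expected losses stay in mITT. If evaluable in section 2.1 means mITT, the four are outside it and the dilution is 0. That also stands, and is why a range is given.

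Third, the dilution is a known fraction for each pattern, and the planned tabulation of missingness would let a reader work it out. This stands in part: the artefact could be removed by calculation afterwards. But an analysis that must first be corrected for its own filling rule is not a test of a missing-data assumption.

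Some stronger readings are tempting but unsupported:

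- **The effect is erased.** A reader might infer this from the zero for periods 2 and 4. It requires a participant to miss period 2, return for period 3 and miss period 4, so permanent dropout cannot cause it. Putting all four losses there would give 4/26 = 15.4%, but nothing in the documents suggests that pattern.
- **The bias is always toward no effect.** With no effect, an assumed worsening of 0.3 points per period and all four losses of period 4 in Sequence A, approach (A) gives −0.018 and observed data −0.044. A time trend can move either estimate off zero.
- **Week-1 ratings distort partial fills by a stated amount.** The averaging rule has no week-2 limit, but the documents give no size for carryover and section 2.1 has a 1-week washout, so no percentage is claimed.

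**Conclusion.** The point holds for approach (A) only. Its whole-period rule crosses treatments whenever period 2 or 4 is filled, halves the affected participant's effect in expectation, and has nothing to carry into period 1. If four of 26 are lost, the trial-level dilution runs from 0 (all outside mITT) to 7.7% (all in mITT and missing only period 4). The per-participant result needs no assumption about dropout timing; the pooled figure depends on it entirely, and the SAP does not give it.

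A reader might infer that the trial's main result is biased. The documents do not support that: the primary model and the completers analysis use no carried-forward values. What is lost is the meaning of a smaller estimate under approach (A), since part or all of the fall would come from mislabelled treatment. The rule should be changed before analysis, but it does not threaten the primary conclusion.

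**What to change.** Delete the cross-period carry-forward in section 2.3. Replace it with multiple imputation of week-2 values from a model with participant, treatment and period. No score then crosses treatments, period 1 is covered, and imputation uncertainty is kept. In simulation with four participants missing period 4 and a true effect of −1, this gives −0.981 against −0.982 on observed data, and 5.1% rejection under no effect for both.

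Copying the participant's other period on the same treatment is not a good substitute. It avoids the mislabelling but treats a copy as new data (6.4% rejection under no effect in the same setting).

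Under missing-at-random, multiple imputation stays close to the primary model by design, so on its own it tests little. Pair it with a tipping-point analysis that adds increasing penalties to missing TJ-68 values, up to the scale maximum of 10, and report where the conclusion changes.

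Fill partly missing periods from week-2 ratings only, in line with the week-2 restriction in section 3.1.

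Cost: SAP wording and modest extra programming. Design, data collection and primary analysis are unchanged.
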